14. EXPOSURE TO ¹⁸F-AV-1451

There is only one scheduled IV bolus injection of ¹⁸F-AV-1451 in this study, unless the subject meets the requirements to undergo a second ¹⁸F-AV-1451 PET (see Section 3.1). For each injection, the net activity administered (mCi) as determined by the PET imaging core laboratory(ies) will be summarized using descriptive statistics for the SAF overall and by most recent neurological disease diagnosis. A similar summary will be presented for the EFF1.

The injection site will be presented in subjects data listing only.

Document:	\\quintiles.net\enterprise\Apps\sasdata\SASa\sas\AVID\18F-AV-1451\Biostatistics\Documentation\SAP\Avid_18F-AV-1451-A16_SAP_Final_v1.0_20180815.docx		
Author:	XXXXXXXXXX	Version Number:	Final, v1.0
		Version Date:	15Aug2018
Template No:	CS_TP_BS016 – Revision 3	Reference:	CS_WI_BS005
Effective Date:	01May2012		

15. EFFICACY OUTCOMES

All efficacy analyses will be performed using the EFF1 or EFF2, as appropriate, unless otherwise indicated.

15.1. PRIMARY EFFICACY

15.1.1. PRIMARY EFFICACY ANALYSIS #1

For the primary efficacy analysis #1, the diagnosis performance (sensitivity/specificity) of 5 independent readers' interpretation of ante-mortem ¹⁸F-AV-1451 PET scan images (AD+/AD++ or AD-; refer to Section 3.2) for detection of a pattern of ¹⁸F-AV-1451 PET neocortical uptake that corresponds to NFT score B3 (Hyman et al., 2012; Montine et al., 2012; refer to Section 3.3) at autopsy will be evaluated.

¹⁸ F-AV-1451 PET Scan Read Result	Autopsy NFT Score TS	
	NFT Score B3 (True Positive)	NFT Score B0, B1 or B2 (True Negative)
AD+/AD++: ¹⁸ F-AV-1451 Neocortical Uptake Consistent with AD Pattern	TP	FP
AD-: ¹⁸ F-AV-1451 Neocortical Uptake Not Consistent with AD Pattern	FN	TN

The sensitivity and specificity along with their two-sided 95% CI (based on the Wilson score method) will be calculated for each of the five readers. The first primary efficacy analysis will be considered to be met if for at least the same 3 out of 5 readers, the lower bound of the 95% CI for both sensitivity and specificity are $\geq 50\%$ (i.e., statistically significant at two-sided significance level of 0.05).

The accuracy, PPV, NPV, LR+ and LR- of the ¹⁸F-AV-1451 PET imaging classification for each of the five readers relative to the autopsy NFT score TS will be also calculated. Two-sided 95% CIs (based on the Wilson score method) will be provided for the accuracy, the PPV and NPV.

Additionally, the number and percentage of subjects for each Braak stage and NFT stage will be provided for each hemisphere overall and by most recent neurological disease diagnosis. The number and percentage of subjects in each highest hemisphere/stain NFT score and autopsy NFT score TS will be summarized overall and by most recent neurological disease diagnosis. A listing of subjects who are autopsy NFT score TS positive and TS negative will be provided including the same information as well as the readers' interpretation of the ¹⁸F-AV-1451 PET scan image(s).

15.1.2. PRIMARY EFFICACY ANALYSIS #2

For the primary efficacy analysis #2, the diagnosis performance (sensitivity/specificity) of 5 independent readers' interpretation of ante-mortem ¹⁸F-AV-1451 PET scan images (AD+/AD++ or AD-; refer to Section

Document:	\\quintiles.net\enterprise\Apps\sasdata\SASa\sas\AVID\18F-AV-1451\Biostatistics\Documentation\SAP\Avid_18F-AV-1451-A16_SAP_Final_v1.0_20180815.docx		
Author:	XXXXXXXXXX	Version Number:	Final, v1.0
		Version Date:	15Aug2018
Template No:	CS_TP_BS016 – Revision 3	Reference:	CS_WI_BS005
Effective Date:	01May2012		

3.2) for detection of a pattern of ¹⁸F-AV-1451 neocortical uptake that corresponds to high levels of AD neuropathologic change as defined by NIA-AA criteria (Hyman et al., 2012; refer to Section 3.3) at autopsy will be evaluated statistically, if and only if the primary efficacy analysis #1 is a success. For individuals with cognitive impairment, high levels of AD neuropathologic change are considered adequate to explain cognitive impairment or dementia symptoms.

NIA-AA Autopsy Diagnosis TS

¹⁸ F-AV-1451 PET Scan Read Result	High AD Neuropathologic Change (True Positive)	No, Low or intermediate AD Neuropathologic Change (True Negative)
AD+/AD++: ¹⁸ F-AV-1451 Neocortical Uptake Consistent with AD Pattern	TP	FP
AD-: ¹⁸ F-AV-1451 Neocortical Uptake Not Consistent with AD Pattern	FN	TN

The sensitivity and specificity along with their two-sided 95% CI (based on the Wilson score method) will be calculated for each of the five readers. The second primary efficacy analysis will be considered to be met if for at least the same 3 out of 5 readers, the lower bound of the 95% CI for both sensitivity and specificity are ≥ 50% (i.e., statistically significant at two-sided significance level of 0.05).

The accuracy, PPV, NPV, LR+ and LR- of the ¹⁸F-AV-1451 PET imaging classification for each of the five readers relative to the NIA-AA autopsy diagnosis TS will be also calculated. Two-sided 95% CIs (based on the Wilson score method) will be provided for the accuracy, the PPV and NPV.

Additionally, the number and percentage of subjects for each Thal phase, Aβ plaque score, atypical tau pathology status, neuritic plaque score (modified from CERAD), and NIA-AA AD neuropathological change will be provided for each hemisphere overall and by most recent neurological disease diagnosis. A listing of subjects who are NIA-AA autopsy diagnosis TS positive and TS negative will be provided including the same information as well as the readers' interpretation of the ¹⁸F-AV-1451 PET scan image(s).

15.1.3. SUPPORTIVE ANALYSIS TO PRIMARY EFFICACY ANALYSES

Primary efficacy analyses #1 and #2 will be repeated based the FAS1/FAS2, as appropriate, and SENS set.

15.1.4. SUBGROUP ANALYSES TO PRIMARY EFFICACY ANALYSES

Primary efficacy analyses #1 and #2 will be repeated for each subgroup specified in Section 7.6.

Document: \\quintiles.net\enterprise\Apps\sasdata\SASa\sas\AVID\18F-AV-1451\Biostatistics\Documentation\SAP\Avid_18F-AV-1451-A16_SAP_Final_v1.0_20180815.docx
 Author: XXXXXXXXXX Version Number: Final, v1.0
 Version Date: 15Aug2018
 Template No: CS_TP_BS016 – Revision 3 Reference: CS_WI_BS005
 Effective Date: 01May2012

15.2. SECONDARY EFFICACY

15.2.1. DIAGNOSTIC PERFORMANCE OF ANTE-MORTEM ¹⁸F-AV-1451 PET IMAGING BASED ON MAJORITY INTERPRETATION OF 5 INDEPENDENT READERS

For each image, the majority interpretation of 5 independent readers will be derived using individual readers' interpretation results. Diagnostic performance of this majority interpretation will be assessed relative to the autopsy NFT score TS as per primary efficacy analysis #1 (refer to Section 15.1.1) and again relative to the NIA-AA autopsy diagnosis TS as per primary efficacy analysis #2 (refer to Section 15.1.2).

The sensitivity and specificity along with their two-sided 95% CIs (based on the Wilson score method) will be calculated for the majority interpretation of 5 independent readers relative to the appropriate TS.

The accuracy, PPV, NPV, LR+ and LR- of the ¹⁸F-AV-1451 PET imaging classification for the majority interpretation of 5 independent readers relative to the appropriate TS will be also calculated. Two-sided 95% CIs (based on the Wilson score method) will be provided for the accuracy, the PPV and NPV.

15.2.2. INTER-RATER AGREEMENT AMONG READERS OF ¹⁸F-AV-1451 PET IMAGING INTERPRETATION

Fleiss' Kappa statistics will be used to assess inter-reader agreement for the diagnostic decision associated with the primary efficacy analysis #1 and #2. For evaluation of agreement in the context of primary efficacy analysis #1, Fleiss' Kappa statistic will be calculated according to the readers' interpretation classification as specified in Section 15.1.1 along with its two-sided 95% CI and associated p-value. A second Fleiss' Kappa statistic will be calculated using the readers' interpretation classification as specified in Section 15.1.2 along with its two-sided 95% CI and associated p-value. Percentage of agreement will also be provided i.e., number of images for which a pair of readers in agreement divided by the total number of images evaluated by any pair of readers multiplied by 100%.

In addition, the agreement between each pair of readers (reader 1 vs. readers 2, 3, 4, and 5 separately; reader 2 vs. readers 3, 4, and 5 separately; reader 3 vs. readers 4, and 5 separately; and reader 4 vs. reader 5) will be assessed for each diagnostic decision using the simple kappa coefficient, its two-sided 95% CI, and associated p-value. Percentage of agreement will also be provided for each pair of reader i.e., number images for which the pair of readers are in agreement divided by the total number of images evaluated by the pair of readers multiplied by 100%.

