3.2. EVALUATION OF ¹⁸F-AV-1451 PET IMAGES

Criteria for declaring an image invalid or not evaluable were specified in advance in the Image Review Charter. In this SAP, valid images will be considered as unevaluable only if at least 3 out of 5 independent readers declare the image unevaluable for the same reason(s).

¹⁸F-AV-1451 retention of PET images were interpreted by visual examination as either

- AD-: neocortical uptake not consistent with an AD pattern i.e., no increased neocortical activity in any region or increased activity is isolated to the mesial temporal, anterolateral temporal or frontal region(s);
- AD+: neocortical uptake consistent with an AD pattern i.e., increased neocortical tracer activity in the posterolateral temporal (PLT), parietal (including precuneus) or occipital region(s); or
- AD++: neocortical uptake consistent with an AD pattern and with likelihood of disease progression i.e., increased neocortical tracer activity is found in the parietal (including percuneus) region(s) regardless of uptake elsewhere (subset of AD+) or in the frontal region in addition to PLT, occipital or parietal region(s).

For the purpose of testing the primary analyses, a scan interpretation will be considered positive (hypothesized to correspond to a B3 NFT score for the first primary efficacy analysis and an NIA-AA score of high AD pathology for the second primary efficacy analysis) if the scan was interpreted as at least consistent with an AD pattern (AD+ or AD++).

Images were also assessed quantitatively (computerized measurement of Standard Uptake Value Ratios [SUVRs]) for exploratory analysis purposes.

The ¹⁸F-AV1451 PET imaging results will not be shared with the investigator sites or subjects and their families prior to the end of the study.

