5.3. MODIFIED INTENT-TO-TREAT ANALYSIS SET

The modified Intent-to-Treat analysis set (mITT) will include all SAF subjects (refer to Section 5.2) recruited under this protocol with available PET Scan visual interpretation data (regardless of PET Scan image validity and evaluability)

This analysis set will be used to conduct the secondary efficacy analysis for the inter-reader agreement among readers (refer to Section 15.2.2). Summaries will be presented according to the individual reader's interpretation of the ¹⁸F-AV-1451 PET image (see Section 3.2 and APPENDIX 1).

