7.3. MISSING DATA

Missing efficacy and safety data will not be imputed with the exception of missing AE severity and missing AE relationship to study medication/procedure (refer to Sections 16.1.1.1, 16.1.1.2, and 16.1.1.3, respectively). Missing or partial AEs and medications dates and/or time will be handle as described in APPENDIX 2.

It is possible that for some cases, only half of the brain tissues was available for pathological analysis while the whole brain ¹⁸F-AV1451 PET scan images were available for visual reads. For these cases, only the visual reads from corresponding side of brain will be used for efficacy analyses.

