7.4. HYPOTHESES TESTING AND MULTIPLE COMPARISONS/ MULTIPLICITY

For the primary analysis of the first primary efficacy endpoint (refer to Section 15.1.1), the hypothesis to be tested is that for at least the same 3 out of 5 independent readers, the lower bound of the two-sided 95% CI for both sensitivity and specificity of ¹⁸F-AV-1451 PET reading interpretations will be $\geq 50\%$.

For the primary analysis of the second primary efficacy endpoint (refer to Section 15.1.2), the hypothesis to be tested is also that for at least the same 3 out of 5 independent readers, the lower bound of the two-sided 95% CI for both sensitivity and specificity of ¹⁸F-AV-1451 PET reading interpretations will be $\geq 50\%$.

This trial will be considered as successful if both primary efficacy analyses reach statistical significance at a two-sided significance level of 0.05.

All other efficacy endpoints (refer Sections 15.2.1, 15.2.2, and 15.3) will be tested without multiplicity adjustments and nominal p-values will be provided. Although nominal p-values will be provided for the secondary efficacy endpoints, the hypothesis to be tested for these endpoints are:

- The majority read results will have the lower bound of the two-sided 95% CI $\geq 55\%$ for both sensitivity and specificity for detection of tau neurofibrillary pathology that corresponds to NFT score of B3,
- The majority read results will have the lower bound of the two-sided 95% CI $\geq 55\%$ for both sensitivity and specificity for detection of a pattern of ¹⁸F-AV-1451 neocortical uptake that corresponds to a high levels of AD neuropathologic change as defined by NIA-AA criteria, and
- The observed kappa values are ≥ 0.64 and the lower bound of the two-sided 95% CIs are ≥ 0.55 for the inter-reader agreement among readers.

No statistical testing will be carried out for disposition and withdrawal (refer to Section 9), demographic or other baseline characteristics (refer to Section 10), medical/surgical history (refer to Section 11), concurrent diseases/conditions (refer to Section 11), prior and concomitant medications (refer to Section 12), exposure to ¹⁸F-AV-1451 (refer to Section 14), other efficacy endpoint (refer to Section 15.4), and all safety outcomes (refer to Section 16).

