7.5.3. FLEISS' KAPPA

The agreement between the five readers will be calculated using Fleiss' kappa along with its 95% CI (Fleiss 1981).

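### As worded, the SAP's overall five-reader percentage of agreement is 100% for every image with at least three usable reads, so it says nothing about agreement

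*SAP*

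**What the plan says.** Agreement among readers is a secondary objective (SAP Section 2.2). Its formal criterion uses kappa. SAP Section 7.5.3 states: "The agreement between the five readers will be calculated using" Fleiss' kappa with a 95% CI. Section 7.4 sets the hypothesis: "The observed kappa values are ≥ 0.64", with a lower two-sided 95% bound of at least 0.55.

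Section 15.2.2 then adds two percentages of agreement.

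- **Overall, five readers:** the "number of images for which a pair of readers in agreement divided by the total number of images evaluated by any pair of readers", times 100%.
- **Each named pair of readers:** the "number images for which the pair of readers are in agreement divided by the total number of images evaluated by the pair of readers", times 100%.

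The reads are in two categories. Section 15.1.1 describes the readers' interpretation of the "PET scan images (AD+/AD++ or AD-; refer to Section 3.2", and Section 15.1.2 uses the same split.

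The agreement analysis uses the mITT set, which keeps images "regardless of PET Scan image validity and evaluability" (Section 5.3), and Section 15.2.3 repeats it on FAS1 and SENS. Section 7.3 says: "Missing efficacy and safety data will not be imputed", with exceptions only for adverse-event severity and relationship. Protocol Section 8.2.2 plans kappa alone for this objective and defines no percentage.

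**The concern.** In the pair-specific definition the pair is fixed in advance, so counting images is right: each image is either a match or a mismatch for that pair. The overall definition keeps the image as the unit but lets the pair be any of the ten. An image then counts as agreement as soon as some two readers match. With more readers than categories, that always happens.

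The result would be a figure that cannot vary with reader behaviour, printed beside statistics that can. A programmer following the SAP would output 100% in up to three tables (mITT, FAS1, SENS), or would have to choose a definition that the SAP does not give. The choice matters, because the natural alternatives give very different numbers.

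**Working it through.** The documents give no value for this percentage, so there is no figure to reproduce. The check is on what the formula returns.

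**Inputs.** Five readers (SAP 7.5.3, 15.2.2); two categories (15.1.1, 15.1.2); kappa target 0.64 (7.4). Assumed: the share of positive reads *p*, from 30% to 70%, and one illustrative mix of splits.

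**Step 1: the formula as written.** An image scores 1 if at least one pair of its readers matches. All possible read patterns were enumerated:

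| Usable reads | Categories | Patterns | Patterns with an agreeing pair |
|---|---|---|---|
| 5 | 2 | 32 | 32 |
| 4 | 2 | 16 | 16 |
| 3 | 2 | 8 | 8 |
| 2 | 2 | 4 | 2 |
| 5 | 3 (AD-, AD+, AD++) | 243 | 243 |

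The ratio is therefore 100% unless some image has exactly two usable reads and they differ. With five readers, that requires three of them to give no usable read on that image. The mITT set and the no-imputation rule allow this case.

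**Step 2: agreement counted over reader pairs.** A fully read image has C(5,2) = 10 pairs.

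- 5-0 split: C(5,2) = 10 agreeing pairs, 100%
- 4-1 split: C(4,2) = 6 agreeing pairs, 60%
- 3-2 split: C(3,2) + C(2,2) = 3 + 1 = 4 agreeing pairs, 40%

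The pooled figure for fully read images can thus lie anywhere from 40% to 100%.

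**Step 3: readers with no skill.** For coin-flip readers the 32 equally likely patterns are 2 of type 5-0, 10 of type 4-1 and 20 of type 3-2.

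- Formula as written: 32/32 = 100%
- Pooled over pairs: (2×10 + 10×6 + 20×4)/(32×10) = 160/320 = 50%
- All five agree: 2/32 = 6.25%

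**Step 4: at the kappa target.** Chance agreement is pe = p² + (1−p)², and pooled pairwise agreement is pe + 0.64 × (1−pe).

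| p (assumed) | pe | Pooled agreement at kappa 0.64 |
|---|---|---|
| 0.5 | 0.50 | 0.50 + 0.64×0.50 = 82.0% |
| 0.4 or 0.6 | 0.52 | 0.52 + 0.64×0.48 = 82.7% |
| 0.3 or 0.7 | 0.58 | 0.58 + 0.64×0.42 = 84.9% |

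The formula as written gives 100% in every row, if each image has at least three usable reads.

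**Step 5: illustration (assumed mix).** For 100 fully read images, 60 split 5-0, 20 split 4-1 and 20 split 3-2, the pooled figure is (60×10 + 20×6 + 20×4)/1000 = 800/1000 = 80%. The formula as written gives 100%.

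**The case against.** The strongest reply is that this is loose wording rather than a wrong rule. The sentence is missing a verb, and it directly follows Fleiss' kappa, whose observed-agreement term is the pooled pairwise agreement. The next paragraph applies the same formula to each pair. The authors probably meant those ten ratios pooled. That is a fair guess at intent, but it needs words that are not there: the text counts images in both places and never says to sum over pairs. Nothing visible elsewhere in the SAP or the protocol supplies the missing step. SAP Section 8 says the table shells set the format and content of the outputs. They are not among the documents, so a clarifying footnote there cannot be ruled out.

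A second reply is that little depends on the figure, and this stands. The percentage has no threshold and no hypothesis. For fully read images every pair has the same denominator, so the pooled figure is the simple mean of the ten pair-specific percentages that are already planned.

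A reader might infer that a reported 100% would pass as evidence of high reliability. The documents do not support that. If agreement were truly 100% and both categories were used, kappa would be (1−pe)/(1−pe) = 1. A 100% beside a kappa near 0.64, or beside any pair-specific percentage below 100%, would contradict the rest of the same section and would probably be noticed.

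**Conclusion.** The point holds for the definition as written. The overall percentage of agreement is fixed at 100% for every image with at least three usable two-category reads, whatever the quality of the reading. At the SAP's own kappa target, the pooled pairwise figure would be about 82% to 85%, for an assumed 30% to 70% of positive reads. So the written rule would overstate it by about 15 to 18 percentage points (100 − 85 and 100 − 82).

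The reach is narrow. It would be wrong to infer that the reader-agreement objective or the trial's success rule is compromised. The Fleiss' kappa criterion (at least 0.64, lower bound at least 0.55), the pairwise kappas, the pair-specific percentages and both primary analyses do not use this figure. Nor is there a miscalculation, since no value is stated. It is a minor defect in a descriptive statistic, worth correcting because the correction is simple.

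The conclusion assumes that the sentence is executed literally and that the unseen shells do not override it.

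**What to change.** Replace the overall definition in SAP Section 15.2.2 with wording such as: *the number of agreeing reader pairs, summed over images, divided by the number of reader pairs in which both readers gave a usable read, summed over images (10 per fully read image), multiplied by 100%.*

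For image *i* with *n* usable reads, of which *a* are AD+/AD++, the numerator term is C(a,2) + C(n−a,2) and the denominator term is C(n,2). An image with fewer than two usable reads contributes nothing. The same sentence then covers incomplete reads on mITT, FAS1 and SENS.

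Check the table shells for the same wording and align them. The cost is one sentence in the SAP and one line of programming. No new data are needed, and no success criterion changes. It should be settled before unblinding, so that the definition is not chosen with results in view.

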15.2.3. SUPPORTIVE ANALYSIS TO SECONDARY EFFICACY ANALYSES

The diagnosis performance of ante-mortem ¹⁸F-AV-1451 PET imaging based on majority interpretation of 5 independent readers analysis will be repeated based on the FAS1/FAS2, as appropriate, and SENS.

The inter-reader agreement among 5 readers of ¹⁸F-AV-1451 PET imaging interpretation analysis will be repeated based on the FAS1 and SENS.

Document:	\\quintiles.net\enterprise\Apps\sasdata\SASa\sas\AVID\18F-AV-1451\Biostatistics\Documentation\SAP\Avid_18F-AV-1451-A16_SAP_Final_v1.0_20180815.docx		
Author:	XXXXXXXXXX	Version Number:	Final, v1.0
		Version Date:	15Aug2018
Template No:	CS_TP_BS016 – Revision 3	Reference:	CS_WI_BS005
Effective Date:	01May2012		

15.2.4. SUBGROUP ANALYSES TO SECONDARY EFFICACY ANALYSES

No subgroup analyses will be performed for the secondary efficacy analyses.

15.3. EXPLORATORY EFFICACY

Descriptive statistics will be presented for the quantitative analysis result of ¹⁸F-AV-1451 PET scan (i.e., SUVr) by most recent neurological disease diagnosis based on the FAS. The reference region for SUVr values will be a selected white matter region derived using a parametric estimation of signal intensity (PERSI) method. The global SUVr assessment will be computed using a data driven target region using multi-block barycentric discriminant analysis (MUBADA) method. The target region for regional SUVr are based on automated anatomical labeling (AAL) atlas.

The objective of exploratory analysis is to find a cut-off value for MUBADA SUVr for each pathological truth standard as defined in Section 3.2 and 3.3 respectively, to define a positive (corresponding to pathological positive) and negative (corresponding to pathological negative) scan using MUBADA SUVr values. For each pathological truth standard, a logistic regression model will be applied using pathological truth standard as the dependent variable and MUBADA SUVr value as independent variable. Receiver operating curves (ROC) will be generated and a Youden’s Index method will be used to select the best cut-off values. The ROC figure and area under the Curve (AUC) of the ROC will be provided as well as its p-value and the SUVr cut-off value.

Additionally, the number and percentage of accurate classification for the TS positive, negative, and both combined will be provided where an accurate classification is defined as follows for TS positive

$$\frac{\text{Number of TS positive subjects with global SUVr value on or above the cut-off value}}{\text{Total number of TS positive subjects}} \times 100\%$$

Similarly, accurate classification for TS negative is defined as follows:

$$\frac{\text{Number of TS negative subjects with global SUVr value below the cut-off value}}{\text{Total number of TS negative subjects}} \times 100\%$$

Finally, accurate classification for TS positive/negative combined is defined as follows:

$$\frac{[(\text{Number of TS positive subjects with global SUVr value on or above the cut-off value}) + (\text{Number of TS negative subjects with global SUVr value below the cut-off value})]}{\text{Total number of TS positive/negative subjects}} \times 100\%$$

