5.4.1. FULL ANALYSIS SET #1

The FAS #1 (FAS1) will include all SAF subjects (refer to Section 5.2) recruited under this protocol that:

- came to autopsy, *including* the Front-Runner Cohort (i.e., including the first three subjects who came to autopsy),
- had valid and evaluable PET data (refer to Section 3.2), and
- had valid and interpretable autopsy specimens (refer to Section 3.3), where interpretability will be assessed for the Braak Stage.

This analysis set will be used to summarize the consensus panel’s assessment of each TS (refer to Section 15.1), conduct supportive analyses to the first primary efficacy analysis (refer to Section 15.1.1) and secondary analysis of majority of readers versus the NFT Score TS (15.2.1) as well as to conduct the exploratory efficacy analysis exception of the logistic regression model for the NIA-AA autopsy diagnosis TS (refer to Section 15.3). Data will be presented according to the individual reader’s interpretation of the ¹⁸F-AV-1451 PET image (see Section 3.2 and APPENDIX 1), majority of readers’ interpretation of the ¹⁸F-AV-1451 PET image (see Section 3.2 and APPENDIX 1) or by most recent neurological disease diagnosis, as appropriate.

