5.4.2. FULL ANALYSIS SET #2

The FAS #2 (FAS2) will include all SAF subjects (refer to Section 5.2) recruited under this protocol that:

- came to autopsy, *including* the Front-Runner Cohort (i.e., including the first three subjects who came to autopsy),
- had valid and evaluable PET data (refer to Section 3.2), and
- had valid and interpretable autopsy specimens (refer to Section 3.3), where interpretability will be assessed for the NIA-AA autopsy diagnosis.

This analysis set will be used to conduct supportive analyses to the second primary efficacy analysis (refer to Section 15.1.2) and majority of readers secondary analysis for the NIA-AA autopsy TS (refer to Section 15.2.1) as well as to conduct the logistic regression model exploratory efficacy analysis for the NIA-AA autopsy diagnosis TS (refer to Section 15.3). Data will be presented according to the individual reader’s or majority of readers’ interpretation of the ¹⁸F-AV-1451 PET image (see Section 3.2 and APPENDIX 1), as appropriate.

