7. STATISTICAL CONSIDERATIONS

7.1. SAMPLE SIZE JUSTIFICATION AND TRIAL STOPPING CRITERIA

Assuming sensitivity/specificity of approximately 80%, a minimum of 14 autopsy cases in each of the TS groups (pathological positive or negative as defined in Table 2 and Table 3) is required for the lower bound of the two-sided 95% confidence interval (CI) to be > 50% for each individual reader.

The Sponsor is blinded to the pathological results (TS) until after the study is completed and the database is locked. Therefore, in order to ensure that an adequate number of subjects were recruited and came to autopsy for each TS group, the Sponsor assumed that subjects diagnosed on clinical grounds as having dementia due to AD are TS positive and subjects diagnosed as having no cognitive impairment (cognitively normal) are TS negative. Based on these assumptions, the study sample size requirement and trial stopping criteria were to be deemed as having been met when:

- the number of subjects diagnosed as having impairment due to AD that came to autopsy was greater than or equal to 14, AND
- the number of subjects diagnosed as having no cognitive impairment that came to autopsy was greater than or equal to 14

The Sponsor recognizes that there might have been some error in clinical diagnosis such that some subjects diagnosed clinically as having impairment due to AD may have non-AD pathology, or limited amounts of AD tau pathology, and thus be TS negative, and less often, subjects considered clinically

Document:	\\quintiles.net\enterprise\Apps\sasdata\SASa\sas\AVID\18F-AV-1451\Biostatistics\Documentation\SAP\Avid_18F-AV-1451-A16_SAP_Final_v1.0_20180815.docx		
Author:	██████████	Version Number:	Final, v1.0
		Version Date:	15Aug2018
Template No:	CS_TP_BS016 – Revision 3	Reference:	CS_WI_BS005
Effective Date:	01May2012		

normal may have AD pathology and thus be TS positive. However, given the excess frequency of cases with AD diagnoses relative to clinically normal subjects recruited in this trial population, any diagnosis errors will likely help ensure a minimum of 14 TS negative subjects without jeopardizing the criterion for TS positive subjects.

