15.3.1. SUPPORTIVE ANALYSIS TO EXPLORATORY EFFICACY ANALYSES

No supportive analyses will be performed for the exploratory efficacy endpoints.

Document:	\\quintiles.net\enterprise\Apps\sasdata\SASa\sas\AVID\18F-AV-1451\Biostatistics\Documentation\SAP\Avid_18F-AV-1451-A16_SAP_Final_v1.0_20180815.docx		
Author:	XXXXXXXXXX	Version Number:	Final, v1.0
		Version Date:	15Aug2018
Template No:	CS_TP_BS016 – Revision 3	Reference:	CS_WI_BS005
Effective Date:	01May2012		

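### SAP 15.3 scores the SUVr cut-off on the subjects used to choose it, so the six classification percentages are optimistic on average and should be labelled apparent and shown beside cross-validated figures

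*SAP*

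**What the plan says.** SAP 15.3 sets out to find an SUVr value that separates positive from negative scans, once for each truth standard. The steps are:

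- Model: "a logistic regression model will be applied using pathological truth standard as the dependent variable and MUBADA SUVr value as independent variable".
- Cut-off: Youden's "Index method will be used to select the best cut-off values".
- Report: "Additionally, the number and percentage of accurate classification for the TS positive, negative, and both combined will be provided". For TS positives the numerator is "Number of TS positive subjects with global SUVr value on or above the cut-off value", and the denominator is all TS positive subjects. The TS-negative and combined percentages are built the same way, with no held-out subjects.

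Three percentages for each of two truth standards make six figures.

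SAP 5.4.1 uses FAS1 to "conduct the exploratory efficacy analysis exception of the logistic regression model for the NIA-AA autopsy diagnosis TS"; SAP 5.4.2 uses FAS2 to "conduct the logistic regression model exploratory efficacy analysis for the NIA-AA autopsy diagnosis TS". Both sets include the front-runners. SAP 15.3.1 adds: "No supportive analyses will be performed for the exploratory efficacy endpoints". Neither document states an internal validation of the cut-off or a rule for tied Youden maxima.

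**The concern.** Youden's index picks the value that maximises sensitivity plus specificity in the sample at hand, so it partly fits that sample's chance features. Scoring the same subjects at that value credits the fit as performance. Since the aim is a cut-off for calling scans positive or negative, a reader will naturally take the percentages as the accuracy to expect in the next patient.

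The trial guards against this elsewhere: front-runners may be used to refine methods and are therefore kept out of the primary analyses. SAP 15.3 does not carry that separation over to the SUVr cut-off. What is at stake is only how six exploratory figures are read.

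**Working it through.** **1. The plan's own figure.** SAP 15.3 gives no number. The relevant size is "a minimum of 14 autopsy cases in each of the TS groups" (SAP 7.1), which was set for the visual readers. With p the observed proportion and z = 1.96, the Wilson lower bound is [p + z²/2n − z√(p(1−p)/n + z²/4n²)] / (1 + z²/n). Taking 80% rounded down to whole cases:

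- 8/10: 49.0%
- 8/11: 43.4%
- 9/12: 46.8%
- 10/13: 49.7%
- 11/14: 52.4%

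So 14 is reproduced. It serves here only as the smallest planned group size.

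**2. Largest set.** SAP 3.1 allows 74 in the primary cohort and reports 3 front-runners, so the full analysis set holds at most 74 + 3 = 77.

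**3. Simulation model (assumed).** TS-negative SUVr is N(0,1) and TS-positive SUVr is N(d,s). Here s is a standard deviation, 1 unless stated, and AUC = Φ(d/√(1+s²)). In each simulated sample, c is the Youden cut-off.

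- Apparent: the sample's own sensitivity, specificity and combined accuracy at c.
- New subjects: Se = 1 − Φ((c−d)/s), Sp = Φ(c), combined = (n₁Se + n₀Sp)/(n₁+n₀).
- Optimism: apparent minus new subjects.

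**4. Worked case.** The cut-off is an observed value; 4,000 samples were run, 300 of them cross-validated with 10 repeats of stratified 5-fold. If best sensitivity = specificity = 80%, then d = 2 × 0.84 = 1.68 and AUC = Φ(1.68/√2) = 0.88. At 90%, d = 2.56 and AUC = 0.965, slightly above the range in step 5. Entries are TS positive / TS negative / combined, in percent.

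| Scenario | Apparent | New subjects | Cross-validated |
|---|---|---|---|
| 80%, 14+14 | 85.1/84.8/85.0 | 75.9/80.0/78.0 | 75.1/79.6/77.3 |
| 80%, 38+39 | 84.6/81.4/83.0 | 79.8/78.1/79.0 | 80.1/78.1/79.1 |
| 90%, 14+14 | 93.7/93.7/93.7 | 85.5/90.5/88.0 | 84.6/90.8/87.7 |
| 90%, 38+39 | 93.2/91.1/92.1 | 89.3/88.9/89.1 | 89.0/89.6/89.3 |

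At 80% the combined optimism is 85.0 − 78.0 = 7.0 points with 14+14 and 83.0 − 79.0 = 4.0 with 38+39. Monte Carlo errors are about 0.1 and 0.06.

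**5. Combined optimism over AUC 0.85/0.90/0.95.** Cut-offs are midpoints averaged over ties, s = 1, with 8,000 samples per cell; splits are TS positive/TS negative.

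- 45/30: 4.0/3.5/3.0
- 37/37: 3.4/3.2/2.6
- 30/45: 4.2/3.5/3.0
- 47/30: 4.2/3.8/3.2
- 14/14: 5.7/5.2/4.3

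The apparent combined figure exceeded the new-subject figure in 77 to 86% of samples. Adding other tie rules and s = 2 widens the ranges to 2.4–4.6 points at 74–75 subjects and 3.7–8.1 at 14/14. Per class they are 2.1–5.6 and 3.3–10.4.

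**6. Unbalanced splits.** SAP 7.1 notes an excess of AD diagnoses and requires only 14 TS-negative cases. At 60/17 and 63/14 (77 subjects), two sets of runs gave TS-negative optimism of 6.8–9.4 and 6.7–9.2 points, and TS-positive optimism of 1.4–2.3 and 1.6–2.5.

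**7. What cross-validation leaves.** With the lowest tied midpoint as the cut-off, the residual bias was at most 0.8 points at 45/30, 37/37 and 14/14. Over all tie rules run at those sizes it reached 1.4 for a single class at 14/14. Root-mean-square error of the combined figure, apparent versus cross-validated, at AUC 0.85/0.90/0.95:

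- 45/30: 5.6/5.4/4.6 versus 5.1/4.9/4.2
- 60/17: 5.7/5.0/4.3 versus 5.9/5.1/4.1
- 63/14: 5.4/5.0/4.1 versus 5.8/5.1/4.3

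The gain near balance therefore disappears in most of the unbalanced cells. There the TS-positive root-mean-square error rose by up to about 2.5 points.

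**The case against.** The strongest reply is that nothing here is an error. SAP 15.3 says it will find a cut-off, defines the percentages by formula, never calls them performance in new subjects, and attaches no decision to them. On that view a one-word label is enough. This stands as a limit on importance. It does not answer the bias, and cross-validated figures show its size, which a label cannot.

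Some stronger readings are tempting but not supported:

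- A reader might take SAP 15.3.1 as a decision against internal validation. Elsewhere in the SAP (15.1.3, 15.2.3) a supportive analysis means a repeat on another analysis set. The section shows no such decision; validation is simply not mentioned.
- A reader might infer that cross-validated figures are always closer to the truth. They are less biased, but step 7 shows no reliable gain in root-mean-square error.
- A reader might rule out leave-one-out altogether. It failed with lowest-value ties in equal groups, but at 45/30 with averaged midpoints it left at most 0.7 points per class. Its performance depends on the tie rule and the split.
- A reader might suppose that the data-driven MUBADA region was derived in these subjects. The SAP does not say.

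The Quantitative Methodology Document (Protocol 8.4), the output shells (SAP 8) and the separate SAP for outside cases (SAP 3.1) were not available and may say more.

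**Conclusion.** The point holds, as a low-cost improvement. All three percentages per truth standard were overstated on average in every scenario run, although a single sample can go the other way. Combined optimism is about 2 to 5 points with 74 to 77 subjects and about 4 to 8 with 14 per group. At 74 to 77 subjects, class-specific optimism is about 2 to 6 points when the groups are near balance. If only 14 to 17 of 77 are TS negative, it is about 7 to 9 points in TS negatives and 1.5 to 2.5 in TS positives.

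These sizes rest on assumed binormal SUVr, AUC 0.85 to 0.95, the splits shown and a fixed MUBADA region. A reader might extend the criticism to the AUC or to trial success. Neither uses the cut-off, so the ROC curve, the AUC and its p-value, the visual-read analyses and the success criteria are untouched.

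**What to change.** Keep the planned cut-off and percentages, and amend SAP 15.3 as follows, with a matching edit to 15.3.1:

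- Label the percentages 'apparent (resubstitution)'.
- Beside them give the same three percentages from stratified 5-fold cross-validation with 100 repeats and a fixed seed. Re-select the Youden cut-off in every training set, and do this separately for FAS1 and FAS2. With 14 per group each fold still holds 2 or 3 cases per class. Moving from 10 to 100 repeats cuts the seed-to-seed standard deviation of the combined figure from 0.8–1.0 to 0.3 points at 14/14.
- State one tie rule for both sets of figures that keeps the cut-off a Youden maximum, such as the lowest tied midpoint. Averaging tied midpoints does not: the average was not a Youden maximum in 30–34% of samples at 37/37.
- State which data the MUBADA region came from. If it was derived in these subjects, cross-validating the cut-off alone does not remove that optimism.

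The cost is a few sentences and a short resampling program, with no new data. The reported accuracy will fall by a few points. The cross-validated figures describe the selection procedure rather than exactly the one final cut-off. They remove nearly all the bias (residual about 1 point or less), but root-mean-square error may not fall and can rise by up to about 2.5 points for TS positives in unbalanced splits.
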